8.5 Deviations from the statistical analysis plan

Any deviations in the analysis of the final data set from the statistical analysis plan will be documented and justified in the final report.

9. STUDY PROCEDURES

The study is divided into four phases as defined below (See Appendix 66 for Schedule of Visits):

Study Phase	Definition
Screening Visit	Obtain Informed Consent. Completion of Pre-Study Survey. Determination of Inclusion and Exclusion criteria (including PHQ-9 questionnaire; Appendix 3), Medical History and Physical, Obtain Concomitant Medications, Weight Loss History, Blood Pressure, Height and Weight, Blood Tests (including a lipid panel, HbA1c, and Urine Pregnancy Test for FOCBP. Dispense and Instruct on completion of Weekly Diary.
Randomization / Enrollment Visit	
Confirm Inclusion/Exclusion criteria has been met, Weight, blood pressure, and AEs/Concomitant Medications assessed. Completion of baseline TFEQ-R18V2 (Appendix 4). Assessment of T6/T7 Dermatomes, UPT for FOCBP (if not done at screening). Completion of pre-enrollment photographs.
 
Randomization of subject. For both groups (control and treatment) train and dispense paper diaries and electronic scale, encourage low-calorie diet for duration of study, provide Diet Resources sheet (Appendix 18.11)
 
In Addition, For Treatment Group only, training) and assessment of use of smart phone app and Elira wearable patch system (Appendix 2); Initiation of therapy and dose adjustment. Provide TENS Clean-Cote Skin Wipes and/or Alcohol Prep Pads and Cetaphil Moisturizing Lotion with instructions on use, following a healthy low-calorie diet, as needed, dispense smart phone app and Elira wearable patch system. ELIRA Device training (Treatment Group). Paper VAS sheets

Therapy Period	
For Control and Treatment Groups: Confirm Inclusion/Exclusion criteria continues to be met, collect blood pressure, AEs, and review Adverse Device Events, paper diary (dispense additional diaries), weight, blood pressure, assess for AE's/concomitant medications, completion of hunger and Completion of TFEQ-R18V2, encourage continuation of low-calorie diet at each scheduled visit. Blood Tests taken at 12 weeks for lipids and HbA1c. Photographs will be taken at 12 weeks .
 
In Addition, For Treatment Group only: assess for Adverse Device Effects at each visit. Collect Elira wearable patch system and smart phone and download data, assess subjects use of electronic diary, completion paper sheets and stimulation sessions at each visit. Dispense smart phone app and Elira wearable patch system at each visit.

End of Study Visit	For Control and Treatment Groups: Collect the weekly paper diary (if subject has not completed the weekly paper diary, he/she will reschedule the end of study visit for one week later to allow time for completion), Physical, weight, blood pressure, assess for AE's/concomitant medications, UPT for FOCBP, blood pressure, completion of PHQ9, TFEQ-R18V2, End of Study Survey, Blood Tests (including a lipid panel and HbA1c) and photography.

	In Addition, Treatment Group only: assess for Adverse Device Effects, collect Elira Wearable patch system and smart phone and download data, assess subjects use of electronic diary completion and stimulation sessions. Assess T6/T7 dermatomes. Complete End of Study Questionnaire.
--	---

9.1 INFORMED CONSENT

Prior to subject participation in this study, the PI or designee must obtain written Institutional Review Board (IRB) approval for the protocol and the Informed Consent Form.

Once the subject's eligibility has been determined, the Investigator or person designated by the Investigator who has been trained to the Protocol, will explain the nature and scope of the study, discuss potential risks and benefits of participation, answer all questions from the subject and ask the subject to participate in the study. The study will be explained to the study subject in lay terms. If the subject agrees to participate, the Informed Consent must be personally signed and dated by the subject and the Investigator or person designated by the Investigator. Any additional persons required to sign the Informed Consent by the IRB will also do so. A copy of the signed and dated Informed Consent must be provided to the study subject. Study subjects will be assured that they may withdraw from the study at any time and for any reason.

Failure to obtain a signed Informed Consent prior to the procedure constitutes a major Protocol deviation.

9.2 SCREENING PROCEDURES

All candidates must be screened for eligibility. A member of the research team assigned to the study should review the subject's medical history to screen for eligibility.

The following tests and procedures must be performed prior to TENS therapy:

- Physical examination, medication history, height, weight and BMI.
- Relevant medical history including subject demographic information and weight loss history.
- Patient Preference Survey and PHQ-9.
- Urine Pregnancy Test (UPT) for FOCBP; blood lipid panel, HbA1c.

9.3 PHYSICAL EXAMINATIONS

A general physical examination will be performed as well as an examination of organ systems (central nervous system [CNS], cardiac, peripheral vascular, pulmonary, musculoskeletal, abdominal, dermatologic and lymphatic). The dermatologic exam will focus on Dermatome T6-T7 site for any active disease, scars, tattoos, or other problems that would make the site unacceptable for the TENS Unit. Depilation by waxing, shaving, chemical depilatories or any other method in the selected application site is not allowed during the study.

9.4 BODY MASS INDEX

Height and weight without shoes will be used to determine body mass index (BMI) in accordance with the BMI Chart^(15,16); Appendix 1) and confirmed by NIH BMI Calculator. Subjects will be encouraged to wear the same or similar clothing at each visit for more consistent weight measurements.

9.5 MEDICAL HISTORY AND DEMOGRAPHICS

A complete medical history evaluation, including surgical history and demographic data (age, gender, race, ethnicity, and highest level of education) and weight loss history will be obtained for each subject.

9.6 VITAL SIGNS

Blood Pressure (sitting position after 3 minutes rest) will be measured.

9.7 MEDICATIONS

All medications must be reported on the appropriate case report form (CRF) through the end of study. Medications must remain stable from Screening/Baseline through the Therapy Phase of the study. The only exception is medications may be changed for subject health or safety reasons (but not specifically to attempt to reduce weight loss or appetite).

9.8 QUESTIONNAIRES

All subjects will be required to complete the Pre-Study Survey and PHQ-9 at screening/baseline visit. All subjects will be required to complete a VAS diary for hunger and fullness according the following schedule: 1 day with 8 entries following enrollment (approximately week 0-1), 1 day with 8 entries following the 4, 8, 12, 16 and 20-week visit (approximately week 4) and 1 day with 8 entries in the last week of the study (approximately week 24). All subjects will be required to complete the TFEQ-R18V2 at enrollment and at each Therapy Visit (Appendix 3). All subjects will be required to complete PHQ9-, TFEQ-R18V2 and End of Study Questionnaire at the last study visit (Visit 8 or early termination visit).

9.9 URINE PREGNANCY TESTS (UPT)

A urine pregnancy test will be done in the clinic for all females of child-bearing potential (FOCBP) prior to enrollment in the study. The results will be recorded. This can be completed either at Screening Visit (Visit 0) or Randomization/Enrollment Visit (Visit 1) and at the end of study visit.

9.10 DIET

Subjects will be encouraged to maintain a healthy lowcalorie diet throughout the study. The study doctor and/or research coordinator will provide guidance to assist the subjects on maintaining the diet.

9.11 ELECTRONIC DAILY DIARY DEVICE

For Treatment Group Subjects only, an Android Smart Phone running a semi-custom daily diary application to capture hunger, calories, and weight will be provided. Subjects will be instructed on use by PI or designee.

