Treatment subjects will be assessed for any adverse device effects (ADE), T6/T7 dermatome assessment, review and download of diary data, and stimulation adjustment (if needed). If skin irritation is present, PI will classify as Mild, Moderate or Severe and confirm system compliance (wipes, lotion, patch rotation, etc.). Mild irritation may require up to 3 days without stimulation. Moderate irritation may require up to 2 weeks without stimulation. Severe irritation may require medical attention and study termination. PI or designee will assess when irritation is present and review for resolution. Treatment subjects will be discharged with the smartphone application and the Elira wearable patch system and instructions on use. Treatment subjects will be instructed to return with the Elira wearable patch system and smartphone app at their next scheduled visit. Treatment subjects may be contacted by PI or clinical coordinator periodically through the trial to address any questions or concerns related to device function.

End of Study Visit 8 (week 24; ± 7 days) – Treatment & Control subjects will be assessed for adverse events, changes to concomitant medications and commitment to exclusion criteria. Physical including weight, requisition for laboratory tests, blood

Protocol #: CD-005; Version #: 4.0

Original Date: May 8, 2018 Revision Date: May 3, 2019

-Confidential-

	
pressure, labs, and urine pregnancy test for FOCBP, and completion of questionnaires (– PHQ9, TFEQ-R18V2, and Patient Preference Survey). Collect, and review paper diaries. This visit may be rescheduled if the paper diaries were not completed the week prior.
 
Treatment Group Only- Complete End of Study Questionnaires- subjects will return the Elira wearable patch system and the smartphone application. Treatment subjects will be assessed for ADEs and have their T6/T7 dermatome area examined. Treatment subjects will be photographed (below the neck) in similar attire to their initial visit for weight loss reference.

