2. STUDY RATIONALE

The purpose of the present study is to determine the safety and effectiveness of stimulation via a wearable patch TENS system of the T6/T7 dermatome on appetite suppression in adult (18 to

Protocol #: CD-005; Version #: 4.0

Original Date: May 8, 2018 Revision Date: May 3, 2019

-Confidential-

65 years of age inclusive), overweight/obese subjects (i.e. a BMI of 25 to 35 kg/m² inclusive^{15, 16}; Appendix 1) who desire to lose weight. The study will seek thus to extend existing data on the use of dermatomal stimulation on obese and morbidly obese patient to subjects who are overweight/obese (i.e. a BMI of 25 to 35 kg/m²^{15, 16}; Appendix 1).

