5. STUDY DESIGN

[figure not shown]
Randomized, adaptive parallel arm study. Subjects will be initially screened during a screening period (1 week, ± 7 days; Figure 2). During this screening period, prior to study procedures being performed, subjects will sign an informed consent form. Then they will have their weight and blood pressure measured, FOCBP will have a pregnancy test, get blood drawn for analysis (blood lipids, HbA1c), and complete patient preference questionnaires. At the end of the screening/baseline period, eligible subjects will be offered the chance to enroll in the study. After enrolling, subjects will be randomized to treatment or control groups.

The Treatment group will be instructed to follow a healthy diet that they will follow for the duration of the study and will receive training on the use of the paper diaries, electronic scale, smartphone app and the Elira wearable patch system. All treatment subjects will be required to stimulate in the office for up to 30minutes to confirm sufficient system training and to acknowledge understanding stimulation settings. A below neck photograph will be taken of the treatment group in requested attire (i.e. biker shorts and sports bra for women, biker shorts for men). Following this, subjects will enter the Therapy Period, for a ~24-week duration. Treatment subjects may be contacted by PI or clinical coordinator to address any questions related to device functionality or compliance. Device usage will be monitored throughout therapy phase to ensure proper functionality and subject safety.

The Control group will be instructed to follow a healthy diet that they will follow for the duration of the study and will receive training on the use of the weekly paper diary and electronic scale. The Control group will not receive the electronic smartphone app or the Elira wearable patch system/components.

At the end of the 3 months of the Therapy Period, all subjects will be assessed for weight loss, blood pressure, blood lipids, HbA1c, and will continue to participate through months 4-6 to confirm the long term safety of the device prior to being terminated from the study. A below neck photograph will also be taken at the 12 week visit.

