5.1 DOSING SCHEDULE

All Treatment Subjects will be trained in required rotation of the patch electrodes every 24h such that it is applied to varying locations on the T6/T7 dermatome. Each active therapy subject will receive up to 40 mA sustained current of stimulation for up to 30 minutes delivered within approximately 30min of meal time (pre-meal breakfast and dinner), not to exceed 75 min daily (including up to 3-5min rescue sessions). Based on tolerance of the therapy, a subject may decrease his or her dose by dropping one of the pre-meal sessions after receiving approval from a clinical coordinator and/or PI. Subjects who do not experience sufficient appetite suppression may also add up to 3 between meal 5min rescue sessions delivered after receiving approval from a clinical coordinator and/or PI. The nominal stimulation dose per day for any subject will thus be 1200 mA (60 minutes at 20 mA) while the maximum dose for any given subject will be 3900 mA (90 minutes at 40 mA and rescue sessions).

During the therapy period, Treatment Subjects will undergo initial assessments to ensure they are familiar with the device, the daily electronic diary, weekly paper diary, and diet options. All subjects (Treatment and Control) will be required to undergo follow-up assessments at least once per every 4 weeks during the study. Additional unscheduled visits per subject will be permitted during the study to address issues related to subject safety. PI and/or clinical coordinator will oversee any adjustments to treatment dosing or stimulation parameters and may contact treatment subjects to address any concerns regarding device functionality.

5.2 DATA COLLECTION:

All subjects will be asked to keep a VAS paper diary (hunger, appetite, weight and diet) in which they will record such values weekly. Subjects will record their diary variables. For treatment

subjects, any adjustments to stimulation session schedule will be recorded within the electronic diary and by clinical coordinators.

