5.3 ASSIGNMENT & BLINDING

Subjects meeting the Inclusion and Exclusion criteria will be enrolled and randomized into either Treatment or Control groups. The randomization algorithm will be blocked to account for site bias and to ensure counterbalance across sites. As this is an open label study, there will be no consideration for blinding.

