7.2 EXCLUSION CRITERIA

- 7.2.1 Subject has any known gastrointestinal disorder that in the opinion of the PI precludes enrollment into the trial.
- 7.2.2 Subject has had a prior bariatric procedure or any previous procedure on the stomach.
- 7.2.3 Subject has any significant multisystem disease in the opinion of the PI.
- 7.2.4 Subject has > 6.5 HbA1c.
- 7.2.5 Subject has significant cardiac arrhythmia, ectopy, or significant cardiovascular disease.
- 7.2.6 Subject has an existing implanted electrical stimulator (e.g., pacemaker, AICD).
- 7.2.7 Subject is a female of child-bearing potential who is pregnant or intends to become pregnant during the trial period.
- 7.2.8 Subject has current and/or a history of cancer within the past 5 years (not including basal cell carcinoma or cervical carcinoma in situ).
- 7.2.9 Subject has had a weight change of \pm 5% of his/her Total Body Weight in the 3 months prior to screening.
- 7.2.10 Subject has a moderate / severe psychiatric disorder.
- 7.2.11 Subject has a diagnosed neurological disease.
- 7.2.12 Subject has a diagnosed eating disorder.
- 7.2.13 Subject has a skin disorder affecting the thoracic dermatomes.
- 7.2.14 Subject has active or /has ever had shingles in the abdominal area.
- 7.2.15 Subject has abdominal surgery or other scars which may interfere with TENS stimulation in the opinion of the PI.
- 7.2.16 Subject is currently enrolled in other potentially confounding research.
- 7.2.17 Subject has known allergic reaction to materials in the TENS electrodes and/or is otherwise unable to tolerate stimulation with the wearable TENS system. This includes known allergies to latex, nickel and/or hydrogels.

- 7.2.18** Subject has a history of sensitive skin, including eczema wheel-and-flare or other skin irritation, per PI discretion.
- 7.2.19** Subject is actively participating or unwilling to discontinue participation in another weight loss program. Subjects may not enroll in paid or unpaid programs that involve in-person or online apps or coaching, beginning new fitness regimens or utilizing meal planning or paid nutritional coaching during the course of the ELIRA study
- 7.2.20** Subject is taking weight loss control medications including but not limited to OTC medications, Metformin, and Belviq. (See Appendix 8)
- 7.2.21** Subject is planning any major medical treatments or surgeries that could cause weight loss.
- 7.2.22** Subject is unable to take anti-nausea medications planned for the study.

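### Only Treatment gets the daily logging app, its visit review, a diet-options check and extra contacts, so a difference supports the Elira system versus diet advice, not TENS stimulation alone

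*Combined protocol and SAP*

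**What the plan says.** **Treatment only.** Section 9.11 supplies the app: "For Treatment Group Subjects only, an Android Smart Phone running a semi-custom daily diary application to capture hunger, calories, and weight will be provided". Section 5 is explicit about the other arm: "The Control group will not receive the electronic smartphone app or the Elira wearable patch system/components". Appendix 6 (footnote 4, treatment group only) schedules training on the electronic diary at Visits 1 to 7 and its collection and review at Visits 2 to 8. The Section 9 table has staff assess electronic-diary use at each visit, again for Treatment only. Section 5.1 adds: "Treatment Subjects will undergo initial assessments to ensure they are familiar with the device, the daily electronic diary, weekly paper diary, and diet options". On contacts, Section 5 says: "Treatment subjects may be contacted by PI or clinical coordinator to address any questions related to device functionality or compliance". The Visit Schedule in the Protocol Summary has a similar provision ("Treatment subjects may be contacted by PI or clinical coordinator periodically through the trial") but ties it to device function, as does Section 5.1.

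**Both arms.** The Visit Schedule gives both arms diet instruction, the Diet Resources sheet and an electronic scale. Section 5.2 asks all subjects for a weekly paper diary covering hunger, appetite, weight and diet. Section 9.10 provides diet guidance to all, and Appendix 6 gives both arms the same visits, with weight measured at each. Exclusion 7.2.19 applies to everyone: "Subjects may not enroll in paid or unpaid programs that involve in-person or online apps or coaching".

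**The question and the analysis.** Section 2 states the purpose: "determine the safety and effectiveness of stimulation via a wearable patch TENS system of the T6/T7 dermatome on appetite suppression". The Study Rationale in the Protocol Summary also words the hypothesis in terms of TENS. Section 5.3 says: "As this is an open label study, there will be no consideration for blinding". No sham arm is described. The co-primary ANCOVA in Section 8.1.4 has a group factor and a baseline covariate.

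**The concern.** The stated question is whether stimulation reduces appetite and weight. The arms differ in stimulation, but also in daily logging of hunger, calories and weight, in staff review of that logging, in a check of diet knowledge, and possibly in contacts about compliance. Each of these could plausibly affect weight or self-reported appetite by itself. The protocol recognises this kind of influence, since it bars all subjects from outside programs built on apps or coaching.

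Whatever these extras contribute is absorbed into the group term of the ANCOVA. No planned analysis separates that contribution from stimulation. At stake is the wording of the conclusion: a positive result could be reported as an effect of TENS when the comparison supports only an effect of the package.

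**Working it through.** **1. What differs between the arms**

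| Element | Treatment | Control | Source |
|---|---|---|---|
| Diet instruction, diet sheet, diet guidance | yes | yes | Visit Schedule; 9.10 |
| Electronic scale | yes | yes | Visit Schedule |
| Weekly paper diary | yes | yes | 5.2 |
| Scheduled visits, weight at each | yes | yes | Appendix 6 |
| Ban on outside app or coaching programs | yes | yes | 7.2.19 |
| Stimulation | yes | no | 5; 5.1 |
| Daily app log of hunger, calories, weight | yes | no | 9.11; 5 |
| Staff review of the electronic diary, Visits 2 to 8 | yes | no | Appendix 6; Section 9 |
| Familiarity check including diet options | yes | not named | 5.1 |
| Optional contacts, including compliance | yes | not named | 5 |

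The last four rows move together with stimulation. Group is the only treatment term in the model, so its coefficient estimates their joint effect.

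**2. The plan's own figure, as background**

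Section 8.2 gives means of 3.5% and 6% TBWL (difference 2.5 points), SD 5, 80% power, 30% dropout and 80 per group. It does not state alpha for this calculation. I assume two-sided 0.05, in line with the two-sided 95% intervals in Section 8.1.1.

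n per arm = 2 × (1.960 + 0.842)² × 5² / 2.5² = 62.8, so 63 evaluable. Then 63 × 1.30 = 82, within two of the stated 80, while 63 / 0.70 = 90. The stated 80 is thus reproduced approximately by the first inflation. The choice of inflation is a separate matter and does not affect this point.

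**3. How much a non-stimulation effect could matter**

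Inputs: 80 × 0.70 = 56 completers per arm; SD 5; two-sided 0.05; true stimulation effect zero. The effect b of the app, review, check and contacts is not in the documents, so I assume 0.5 to 1.5 points of %TBWL.

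Standard error of the difference = 5 × √(2/56) = 0.945. Noncentrality = b / 0.945, with 110 degrees of freedom.

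| Assumed b (points) | Share of planned 2.5 | Noncentrality | Two-sided rejection, noncentral t | Normal approximation |
|---|---|---|---|---|
| 0 | 0% | 0 | 5.0% | 5.0% |
| 0.5 | 20% | 0.53 | 8.2% | 8.3% |
| 1.0 | 40% | 1.06 | 18.2% | 18.5% |
| 1.5 | 60% | 1.59 | 35.0% | 35.5% |

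These figures cover %TBWL only. Section 8.1.4 also declares success if any one of four self-reported appetite scores is significant. The documents offer no basis for a corresponding calculation on those.

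**The case against.** The strongest reply is that the app belongs to the device under test. The Description of Components in the Protocol Summary says the phone application directs therapy and includes a diary. Section 3 lists the electronic diary as part of the TENS System, and Section 4 couples the patch system with an integrated weight loss strategy. System against diet advice is a legitimate device comparison. This stands, and it is why the comparison remains valid. What it does not cover is the wording in the Study Rationale, in Section 2 and in the second sentence of Section 4, which speak of TENS or stimulation.

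Several stronger readings are tempting but not supported:

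- *Control alone is barred from apps.* Exclusion 7.2.19 binds both arms and concerns enrolling in outside programs. The imbalance comes from what the study itself supplies.
- *Control does no self-monitoring.* It has the scale and the weekly paper diary. The contrast is daily electronic logging with review against weekly paper. It is fair to add that the paper form in Appendix 5 shows appetite and craving scales but no calorie or weight field.
- *The extra contacts are coaching.* They are optional, and two of the three places that mention them tie them to device function. Only Section 5 adds compliance, and nothing shows that they deliver diet advice.
- *App-set meal times are a further confounder.* They schedule the pre-meal sessions and so are part of the intervention.
- *The calorie and weight logs serve no purpose, so removing them is free.* The cross-validation endpoint uses only hunger scales. However, Section 6.2 mentions dietary compliance data, Section 8.3 sets look-back rules for missed dietary entries, and use errors with the dietary application are an ancillary endpoint.

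**Conclusion.** The concern holds as a limit on attribution. As planned, a difference in %TBWL or appetite at 3 months would support an effect of the Elira system (patch, app and associated support) compared with diet advice. It would not isolate TENS stimulation, which the Study Rationale and Section 2 name as the effect under test.

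A reader might infer that the trial cannot be interpreted at all, or that its false-positive rate is known to be 8% to 35%. Neither follows. The package comparison is sound in this respect, and the percentages depend entirely on an assumed shift of 0.5 to 1.5 points, together with 56 completers per arm, SD 5 and two-sided 0.05. They show that a modest non-stimulation effect would matter, not that one exists. The app screens in Appendix 7 are not shown in the available text, so whether the app gives feedback beyond data capture is unknown.

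**What to change.** 1. In Section 5.1 and the Section 9 table, give Control the same diet-options familiarity check at Visit 1.
2. In Section 5, limit the Treatment-only contacts to device function, as the Visit Schedule already does, and log each contact. Safety contacts and unscheduled safety visits are unaffected.
3. Restate the hypothesis in the Study Rationale, the purpose in Section 2, the stimulation sentence in Section 4 and the planned conclusion as the effect of the Elira system compared with diet advice.

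Cost: protocol wording, a simple contact log, a few more minutes at Visit 1 for Control, and a narrower claim.

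Matching the logging itself is optional, either by disabling calorie and weight entry in the Treatment app or by giving Control an equivalent log. The first alters the system being tested and the second adds resources. Neither removes open-label expectancy, which bears most on the self-reported appetite scores, so item 3 is needed in any case.
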